317 We plan on 132 subjects completing the study at three clinical sites. Based on our experience with
318 similar studies, we estimate an expected 17.5% screen failures, dropouts or withdrawal due to the data
319 collection and eligibility requirements. Therefore, up to 160 subjects may sign consent for the main
320 study. Every effort will be made to recruit a broad range of ages into the study.
321

322 **1.3.5 Main Study Treatment Groups**
323 Following the initial 2 weeks of baseline blinded CGM data, subjects will be randomized in a 2:1 ratio
324 to either CGM+DSS or CGM alone.
325

326 **1.3.6 Main Study Visit and Phone Contact Schedule**
327 Subjects will have a Screening Visit with a baseline central HbA1c. They will then complete a 2-week
328 period of blinded study CGM and glucometer use to characterize baseline glycemic control. During
329 this time, they will use their home insulins dosed according to their pre-defined home parameters for
330 carbohydrate counting.
331

332 Eligible subjects will complete baseline questionnaires and be randomized to either CGM+DSS or
333 CGM alone for the remainder of the study. All subjects will continue to use the study CGM
334 (unblinded) and study glucometer and will be transitioned to the study basal insulin pens (Tresiba®
335 [insulin degludec] 100 U/mL) per product guidelines. For meal insulin, subjects with average total

336 daily insulin (TDI) <60 U/day will use NovoLog® (insulin aspart) pens capable of 0.5U increment
337 dosing and subjects with average TDI \geq 60 U/day will use NovoLog® (insulin aspart) pens capable of
338 1.0U increment dosing. All subjects will receive insulin pen training including pen differentiation
339 training. The differences between the pen for Tresiba® (insulin degludec) and for NovoLog® (insulin
340 aspart) will be emphasized to the patient. The training will include the explanation of the user
341 interfaces of both the insulin pens and inControl Advice and how the equipment interacts with the
342 other.

- 343 • Participants in the CGM+DSS group will be trained on the inControl Advice APP and will use
344 it for insulin dose calculations for the remainder of the study.
- 345 • Participants in the CGM alone group will use their pre-defined home carbohydrate counting
346 parameters for insulin dose calculations for the remainder of the study.

[figure not shown]
347
348 All participants have the same post-randomization clinic visit and phone contact schedule, with the

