577 **3.1 Pilot Testing Overview**

578 Prior to outpatient use of substantially changed or updated DSS system components (as deemed
579 by the FDA), we will conduct a pilot study of 2-5 subjects using CGM+DSS under supervision.
580 These subjects will have an approximately 48-hour visit to an outpatient transitional setting such
581 as a hotel. The subjects will be monitored continuously with remote monitoring and will be
582 supervised by study staff with medical personnel (e.g. nurse, EMT, physician) available during
583 the entire visit. Subjects will eat at restaurants or take-out meals and participate in at least 45
584 minutes of activities such as walking or shopping each day. If there are no device anomalies or
585 malfunctions and no device-related adverse events during the pilot testing, the DSS may be
586 deployed for home use. Pilot testing may be repeated as needed after addressing software or
587 device anomalies until successful pilot testing occurs.

588

589

590 **4 2-WEEK BLINDED CGM**

591

592 **4.1 2-Week Blinded CGM Overview**

593 Prior to randomization, the subject will initiate 2 weeks of home use of blinded CGM for
594 characterization of baseline glycemic control and collection of baseline CGM data.
595 The subject will use carbohydrate counting per their usual routine with their usual home insulins
596 during this time.

597 The subject will receive supplies for blood glucose and ketone testing during this period:

- 599 • Blood glucose testing
 - 600 ○ Subjects will be provided with a study blood glucose meter, test strips, and
 - 601 ○ standard control solution to perform quality control (QC) testing at home per
 - 602 ○ manufacturer guidelines.
 - 603 ○ All study blood glucose meters will be QC tested during all office visits. A tested
 - 604 ○ meter will not be used in a study if it does not read within the target range at each
 - 605 ○ concentration per manufacturer labeling. The subject will be instructed to contact
 - 606 ○ study staff for a replacement of the meter, test strips, and control solution if a
 - 607 ○ meter fails QC testing at home.
 - 608 ○ The blood glucose meter training will include instructions to follow labeling
 - 609 ○ instructions with regards to the glucose meter and test strips.
 - 610 ○ Subjects will be reminded to use the study blood glucose meter for all fingerstick
 - 611 ○ blood glucose measurements during the trial.

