 - 612 ○ Subjects will be given guidelines for treatment of low or high blood glucose
 - 613 ○ Subjects will be asked to perform fingerstick BG testing according to the CGM
 - 614 ○ manufacturer guidelines and as needed to follow study guidelines for the
 - 615 ○ treatment of low or high blood glucose.
- 616 • Blood ketone testing
 - 617 ○ Subjects will be provided with a study blood ketone meter and test strips. All
 - 618 ○ study blood ketone meters will be QC tested at the start of the study with at least
 - 619 ○ two different concentrations of control solution if available. A tested meter will

620 not be used in a study if it does not read within the target range at each
621 concentration per manufacturer labeling.
622 o All study blood ketone meters will be QC tested during all office visits. A tested
623 meter will not be used in a study if it does not read within the target range at each
624 concentration per manufacturer labeling. The subject will be instructed to contact
625 study staff for a replacement of the meter, test strips, and control solution if a
626 meter fails QC testing at home.
627 o Subjects will be instructed to perform blood ketone testing as described in Section
628 7.1.2.2.
629 o Subjects will be given guidelines for treatment of elevated blood ketones
630 • Subjects will be required to have a home glucagon emergency kit. Subjects who currently
631 do not have one will be given a prescription for the glucagon emergency kit.
632

633 **Blinded CGM Use**

634 At the screening visit, a CGM sensor will be placed. For subjects not currently using a CGM, the
635 study CGM receiver will be blinded so that the participant is not able to see the CGM glucose
636 values. The participant will be instructed on sensor use including insertion of a new sensor as
637 recommended by the manufacturer (or sooner if the sensor comes out). Additional sensors will be
638 provided. Subjects that currently use a CGM may use the study CGM in the unblinded mode to
639 maintain usual care.
640

641 Participants will be informed that in order to be eligible for the randomized trial, the study CGM
642 must be used on a minimum of 10 out of 14 days.
643

644 **4.1.1 Blinded CGM Use Assessment**

645 Enrolled participants will return approximately 19 ± 5 days after screening to assess the blinded
646 CGM wear. The purpose of the visit will include the following:
647

- 648 • Assessment of compliance with the use of the CGM

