719 Subjects will be provided with study supplies and will be asked to perform fingerstick blood
720 glucose measurements a minimum of four times daily for the first 2 weeks of using the study
721 insulins (premeal and bedtime, for CGM calibrations, to confirm low or high CGM alarms, and
722 for symptoms of low or high blood sugar). Thereafter, subjects will be asked to perform
723 fingersticks in accordance with the labeling of the study CGM device and as needed to follow
724 study guidelines for the treatment of low or high blood glucose. Subjects will continue to use the
725 study basal and meal insulin pens for the remainder of the study.

726 727 **5.1.1 CGM Training**

728 The participant will be provided with sensors and instructed to use the CGM daily for the
729 remainder of the trial. Depending on the subject's prior CGM experience, the subject will have
730 approximately 1 hour of training on how to use CGM for daily diabetes management using the
731 manufacturer's training materials. Product labeling for the Dexcom G5 mobile system states that
732 it is indicated for the management of diabetes in persons age 2 years and older. It is designed to
733 replace fingerstick blood glucose testing for diabetes treatment decisions. Per the product
734 guidelines, fingersticks are required for calibration, or if symptoms or expectations do not match
735 readings, or when taking medications containing acetaminophen.

736
737 During the CGM training session, subjects will view the interactive Dexcom G5 mobile training
738 tutorial that is available on the Dexcom website:
739 (https://s3-us-west-2.amazonaws.com/dexcommisc/tutorial/story_html5.html). Of relevance,
740 proper calibration timing and technique is described in the training tutorial. This training session
741 also covers but is not limited to the following topics:

- 742 • Dexcom G5 mobile components
- 743 • Display device options
- 744 • Setting high/low alerts
- 745 • Inserting sensor
- 746 • Starting sensor session
- 747 • Entering BG meter value
- 748 • Ending sensor session

749 750 **5.1.2 Randomization**

751 Eligible subjects will be randomly assigned to one of two treatment groups:

- 752 1. CGM+DSS Group
- 753 2. CGM alone Group

754
755 Subjects randomized to CGM+DSS will complete an additional baseline questionnaire:

756 • Technology Expectations Survey
757

758 **5.1.3 CGM Data Downloads**

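### Current CGM users may run in unblinded, and prior CGM use is neither a stratum nor a model term: this adds avoidable noise to HbA1c and change-from-baseline comparisons, but no bias to the primary test

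*Combined protocol and SAP*

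**What the plan says.** The run-in is described in two ways.

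- **Blinded for all.** Section 1.3.5: "Following the initial 2 weeks of baseline blinded CGM data, subjects will be randomized in a 2:1 ratio". Section 4.1, opening paragraph: "Prior to randomization, the subject will initiate 2 weeks of home use of blinded CGM for" the "characterization of baseline glycemic control and collection of baseline CGM data". Section 1.3.6 and the blinded-CGM row of Table 1 make no exception either.
- **Blinded for some.** Under the Blinded CGM Use heading in 4.1, the sentence that blinds the receiver opens "For subjects not currently using a CGM, the" and so covers non-users only. The same paragraph adds: "Subjects that currently use a CGM may use the study CGM in the unblinded mode to" keep to their usual care.

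The eligibility and exclusion lists (2.2.1, 2.2.2) neither require nor exclude current CGM use and set no washout, so both kinds of subject can enter. After randomisation everyone wears the sensor unblinded (1.3.6).

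On allocation, section 5.1.2 says only: "Eligible subjects will be randomly assigned to one of two treatment groups". No stratification factor is named. Section 10.2 specifies a repeated-measures ANOVA of monthly percent in range with the group by period interaction as the test. Section 10.3 uses the same type of model for the secondary outcomes, with two measures for HbA1c. Neither contains a term for prior CGM use. The only stated use of that history is in 5.1.1, where the length of CGM training depends on it. Section 10 defers a detailed analysis plan to a later document.

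**The concern.** The trial asks what DSS adds to CGM. For a subject new to CGM, the step from baseline to follow-up includes starting real-time CGM. For a current user it does not. If starting CGM changes glucose control, change from baseline is a mixture of two distributions, and a difference between arms in the share of current users moves the comparison of changes.

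The analysis most clearly exposed is HbA1c. It is measured at screening and at week 12 only (Table 1), and section 2.4.1 says the screening value will serve the endpoint analyses. With two measures, the group by period test is a comparison of change. Also exposed are any CGM analysis that uses the run-in as a baseline, including the ANCOVA that 10.4 cites as already described although no such model appears, and the interim on the first 40 subjects (10.7), where imbalance in prior use can be larger.

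**Working it through.** **The plan's own figures.** Inputs from 10.1: effect size 0.15 (taken as Cohen's f; the metric for this value is not named), N = 132, two groups, three measures, correlation 0.5. Alpha is not stated; 0.05 is assumed.

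- λ = f²·N·m/(1 − ρ) = 0.0225 × 132 × 3 / 0.5 = 17.82 on 2 and 260 df, power 97.2%.
- Allowing for 2:1 allocation, effective N = 4 × 88 × 44 / 132 = 117.3, λ = 15.84, power 95.3%. The stated 95.6% is reproduced closely enough.
- Enrolment: 132 / (1 − 0.175) = 160, as stated.

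**Does the run-in enter the stated tests?** Three monthly measures fill 12 weeks, and a 2-week run-in is not a month. The variability analysis has six 2-week periods, again 12 weeks. So the CGM tests as written appear to use post-randomisation data only. HbA1c does use a pre-randomisation value.

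**Assumptions not in the documents.** Share of current users p = 0.2 to 0.5; shift g from starting CGM = 5 to 10 points of time in range in new users and none in current users; SD of change 10 points.

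**Chance imbalance in prior use.** SE = √[p(1 − p)(1/n₁ + 1/n₂)]; the 95% range is ±1.96 × SE. The interim at 2:1 is about 27 v 13.

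| | p = 0.2 | p = 0.5 |
|---|---|---|
| 88 v 44 | SE 0.0739, ±14.5 points | SE 0.0923, ±18.1 points |
| 27 v 13 | SE 0.135, ±26.5 points | SE 0.169, ±33.1 points |

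An exact hypergeometric calculation at 88 v 44 gives a 16% (p = 0.2) to 36% (p = 0.5) chance of a difference of at least 10 percentage points.

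**Added variance of change.** p(1 − p)g², against 10² = 100:

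| | g = 5 | g = 10 |
|---|---|---|
| p = 0.2 | 4 (4%) | 16 (16%) |
| p = 0.5 | 6.25 (6%) | 25 (25%) |

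**The shift and the variance are one effect.** Without the mixture, the SE of the arm difference in change is 10 × √(1/88 + 1/44) = 1.846.

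- Low corner: imbalance contributes 0.0739 × 5 = 0.37, and √(1.846² + 0.37²) = 1.88. The variance route gives √104 × 0.1846 = 1.88.
- High corner: imbalance contributes 0.0923 × 10 = 0.923, and √(1.846² + 0.923²) = 2.06. The variance route gives √125 × 0.1846 = 2.06.

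The corresponding 95% range for the shift is ±1.96 × 0.37 = ±0.7 to ±1.96 × 0.923 = ±1.8 points. It is already inside the larger SE. The percentages depend only on p and g/SD, so they carry over to HbA1c only if starting CGM shifts HbA1c by half to one SD of change.

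**Which model term helps?** Let x be prior use. A main effect adds βx to every measure on a subject, so it cancels from y₂ − y₁ and from every other within-subject contrast. With complete data the group by period F is unchanged. Only a prior-use by period term, or adjustment in a model for change, removes the mixture.

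**The case against.** The strongest reply has five parts.

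1. **The primary test does not use the run-in.** This stands. A reader might take the ±0.7 to ±1.8 points as an error in the primary result. It belongs to a change-from-run-in comparison that the plan does not state.
2. **Randomisation removes bias.** This stands. Prior use is independent of arm in expectation, and chance imbalance is part of the standard error. Simulation of the unadjusted comparison of changes under the assumptions above gave a type I error of 4.8% to 5.0%. The loss is precision, not validity.
3. **The baseline has one meaning, usual care.** This is fair as a description, and HbA1c is drawn at screening, before any run-in sensor data, so receiver mode cannot affect it. But usual care with and without CGM leaves different room for change once everyone has real-time CGM. The route is prior use rather than blinding.
4. **Current users may, but need not, be unblinded.** This stands, so prior use and receiver mode are separate facts and both should be recorded.
5. **The detailed analysis plan is still to come, and 5.1.2 is only brief.** This stands in part. Silence is not a decision to ignore prior use, and a later plan can add a model term. It cannot stratify subjects who are already randomised.

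**Conclusion.** The concern holds as a modest inefficiency plus an inconsistency of wording. The blinded-for-all statements conflict with the exception in 4.1. Prior CGM use, known at screening because it bears on receiver mode, is used in neither the stated randomisation nor the stated models.

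On the assumed ranges, the variance of change rises by 4% to 25% and the SE of the arm difference goes from 1.85 to between 1.88 and 2.06 points. The 25% needs both a 50:50 mix and a 10-point shift, so it is the extreme case. At the interim the imbalance in prior use may reach about ±26 to ±33 percentage points, but the SE of the comparison grows in the same proportion.

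A reader might infer that the mixed run-in biases the primary comparison or makes the baseline unusable. The documents support neither: the primary measures appear to be post-randomisation only, and allocation is random. What is affected is the HbA1c comparison, any baseline-adjusted or change-from-run-in CGM analysis, and the interim. The share of current users, the shift and the SD are all assumptions.

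**What to change.** - **Screening:** record prior CGM use (yes/no) and the receiver mode worn in the run-in.
- **5.1.2:** stratify the 2:1 randomisation by prior CGM use.
- **10.2 and 10.3:** include prior CGM use together with its interaction with period, or as a covariate in a change or ANCOVA model. A main effect alone would leave the group by period test as it is. HbA1c is where this matters most.
- **1.3.5, 1.3.6, Table 1 and 4.1:** reconcile the text to say that current CGM users may be unblinded during the run-in.

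If enrolment has begun, leave the randomisation alone and rely on the prior-use by period term.

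The cost is set-up of the randomisation list and a few of the 260 error degrees of freedom. No visits, tests or subjects are added, N stays at 132 and enrolment at 160, power is essentially unchanged, and the allowance for current users can remain.
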